Outcomes: Gait efficiency will be assessed with the six-minute walk test (6MWT),²⁵ gait parameters (i.e., velocity, stride length, swing time, double support, and their coefficients of variability) using GAITRite,²⁶ gait safety using counts of observed episodes of stumbles and/or loss of balance, and participants' perceived ease of walking as indicated on a visual analog scale (100 mm line with anchors "Not at all easy" on the left end and "Extremely easy" on the right end). The GAITRite System[®] (CIR systems, Inc.: Havertown PA) is a 4.88 m electronic walkway with sensors arranged in a gridlike pattern to capture footfall contacts. The application software (version 3.9) processes the raw data into footfall patterns and computes spatial and temporal parameters. Participants will walk at a normal, comfortable pace across the walkway for 4 trials. The first trial under each condition will be a practice trial and the data from the remaining three trials for each condition will be averaged. **Aim 2:** All individuals (n=46) will participate in this part of the study. **Intervention:** After undergoing the pre-assessment, participants randomized to the Trained group will be fitted with the HWA device in their home by a research physical therapist. They will be directed to walk with the device on and the therapist will adjust the settings until a safe gait pattern is obtained. The initial setting used will be the one that produced the safest walking at the pre-assessment. Adjustments will be made based on the response to this initial setting. Participants who achieve a safe gait pattern will receive physical therapist supervised home and community-based walking training wearing the HWA device 2 times per week for 45-60 minutes for 8 weeks. Training will consist of walking in and outside of the home while encouraging larger and more symmetrical steps with practice of activities (e.g., multi-directional stepping, turning, navigating around obstacles) that challenge the person's balance and motor control. Rest breaks will be allowed as needed. If the therapist is unable to adjust the HWA to provide a safe gait pattern, the session will be ended and the device removed. The Untrained group will continue their usual daily activities including any exercise regimen that they typically perform. However, they will be asked not to start any new exercise program during the study period.

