we will enroll 23 patients per group for Aim 2. **Data Analysis:** The primary outcome for Aim 1 is the change in gait velocity with and without the use of the HWA device. This analysis will compare the difference in gait velocity using a paired t-test. The test of the with/without HWA gait change will be two-sided and at the 0.05 level. Exploratory analyses may consider associations of difference with patient characteristics such as Hoehn & Yahr stage. Secondary outcomes for Aim 1 will be analyzed similarly using appropriate methods for paired data. The primary outcome for Aim 2 is gait velocity at 8 weeks. The primary analysis will follow intention to treat principles to preserve the balancing properties of randomization.^{29,30} The primary analysis will assess the effect of treatment on gait velocity at 8 weeks using a linear regression model that includes an indicator of treatment, stage, and baseline gait velocity. The test of the treatment effect will be two-sided and conducted at the 0.05 significance level. Sensitivity analyses will examine the per protocol population (those who followed the assigned treatment correctly) and will utilize methodology for handling missing data (i.e., multiple imputation) to account for loss to follow-up.

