Exploratory analyses may explore differences in the treatment effect across baseline patient characteristics (such as Hoehn & Yahr stage). Secondary outcomes for Aim 2 will be assessed similarly to the primary outcome using appropriate generalized linear models. **Interim Monitoring** We will conduct an interim analysis to ensure that the rate of patients in the treatment arm unable to attain a safe gait is not unacceptably high. We will evaluate the failure rate after 10 patients in the treatment arm complete the study. If 5 or more of the 10 patients fail to attain a safe gait with the device, the study will stop to determine if termination is warranted. Assuming an acceptable failure rate is 20%, we would have a 62% chance of correctly stopping the study early with an observed failure rate of 0.5. With the same assumptions, we also have a 3% chance of incorrectly stopping the trial. According to Honda R&D personnel, all participants who have met inclusion criteria during studies with the device have been able to safely use the device during walking. Therefore, the failure rate of 20% is an estimation and not based on preliminary findings. We will also conduct an interim analysis of data to ensure data quality and refine data analysis processes at the end of 12 months.

[figure not shown]

Figure3. Study Flowsheet

References

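### The Aim 2 per-protocol analysis, read naturally, excludes safe-gait failures from the Trained arm only; add a complier-average estimate that keeps the randomised comparison

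*Combined protocol and SAP*

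**What the plan says.** The document is the combined protocol and SAP.

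- **Data Analysis, Aim 2.** "The primary analysis will follow intention to treat principles to preserve the balancing properties of randomization". Week-8 gait velocity is analysed "using a linear regression model that includes an indicator of treatment, stage, and baseline gait velocity". The sensitivity analyses use a per-protocol population, defined only by the parenthesis "those who followed the assigned treatment correctly", and methods that "will utilize methodology for handling missing data (i.e., multiple imputation) to account for loss to follow-up".
- **Intervention, Aim 2.** Training depends on passing a gate: "Participants who achieve a safe gait pattern will receive" the supervised sessions. If the therapist cannot obtain a safe gait, "the session will be ended and the device removed". The Untrained arm has no such gate. It keeps its usual activities and is asked not to take up new exercise.
- **Procedures, Aim 1.** Safe gait means no more stumbles or losses of balance with the device than the same person has without it. Only the Trained group does this part, so that the Untrained group is not exposed to the device.
- **Interim Monitoring.** The stopping rule is introduced with "Assuming an acceptable failure rate is 20" percent. The section adds that this rate is an estimate without preliminary data behind it, and that all eligible participants in earlier device studies used the device safely.

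**The concern.** A per-protocol set preserves a fair comparison only if the same kind of person is removed from each arm. Here one reason for removal, failing the safe-gait gate, exists in the Trained arm alone. The Untrained arm contains people who would also have failed, but nobody identifies them and they stay in. If failing the gate says anything about week-8 velocity that baseline velocity and Hoehn & Yahr stage do not already capture, the per-protocol contrast differs from zero even when training does nothing.

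What is at stake is how the supporting analysis is read. A per-protocol estimate larger than the intention-to-treat estimate would usually be taken to show what the device does for those who can use it. In this design part of that gap could be selection.

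**Working it through.** **The plan's own figures.** They reproduce. A two-sided two-sample t-test with 18 per group and 0.96 SD has power 0.799 (stated: at least 80%). 18/0.8 = 22.5, rounded up to 23 per group. In Interim Monitoring, the chance of 5 or more failures in 10 is 0.033 at a true rate of 20% (stated 3%) and 0.623 at 50% (stated 62%).

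**Inputs for the bias**
- From the plan: 18 evaluable per arm; 20% failure, so 0.20 × 18 = 3.6, taken as 4; a model adjusted for baseline velocity.
- Assumed, because the plan gives no values: correlation of baseline with week-8 velocity ρ = 0.7; correlation r between the tendency to pass the gate and the part of week-8 velocity not explained by baseline, r = 0.3 to 0.5. Week-8 velocity is scaled to SD 1, and the k Trained participants with the lowest tendency to pass are the failures.

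**Formula.** With no treatment effect,

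bias ≈ r × √(1 − ρ²) × S_k / (18 − k),

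where S_k is the sum of the k largest expected normal scores in a sample of 18. Removing the k lowest raises the mean of the rest by S_k/(18 − k).

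- √(1 − 0.49) = 0.714.
- k = 4: S = 1.820 + 1.350 + 1.066 + 0.848 = 5.084, and 5.084/14 = 0.363.
- k = 1: 1.820/17 = 0.107.

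| Failures | r | Per-protocol bias (SD) |
|---|---|---|
| 4 | 0.5 | 0.5 × 0.714 × 0.363 = +0.13 |
| 4 | 0.3 | 0.3 × 0.714 × 0.363 = +0.08 |
| 4 | 0 | 0 |
| 4 | −0.3 | −0.08 |
| 1 | 0.5 | 0.5 × 0.714 × 0.107 = +0.04 |

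Simulation of the same set-up agrees. At r = 0.3 and 0.5 with 4 failures, the nominal 5% per-protocol test rejects about 6% and 8% of the time under no effect. Intention to treat with everyone measured and the complier-average estimate both centre on about 0.

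**Range.** A large-sample check at 20% failure, with ρ from 0.70 to 0.85, gave an adjusted bias of about 0 when failure depends only on baseline speed, and +0.06 to +0.13 SD when failure also predicts a worse week-8 residual. The upper end was about +0.04 SD at 5% failure and +0.18 SD at 30%.

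**With a real effect.** If training adds 0.96 SD in those trained and 4 of 18 fail, intention to treat estimates 0.96 × 14/18 = 0.75 SD. The complier-average estimate divides this by the difference in uptake, 14/18 − 0, and returns 0.96. The per-protocol estimate is about 0.96 + 0.08 = 1.04 at r = 0.3 and 0.96 + 0.13 = 1.09 at r = 0.5.

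**Precision at 4 failures**
- Per-protocol: 0.714 × √(1/14 + 1/18) = 0.254, about 0.26 when simulated.
- Complier-average: 0.714 × √(2/18) ÷ (14/18) = 0.306, about 0.31.

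**The case against.** **A reader might infer that those who fail are the less stable walkers, so the bias must favour the device.** The documents do not support this. The definition in Procedures is within-person: a steady walker can fail on a small increase in stumbles, and a frequent stumbler can pass if the device makes nothing worse. Failure measures response to the device. It may well go with frailty, but the direction is an assumption, and a negative correlation reverses the sign.

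**A reader might also infer that failures have no week-8 visit, so that intention to treat is the same selected comparison.** That is not supported either. The Aim 2 text puts all 46 in this part of the study, the Outcomes text schedules assessments before and after the 8 weeks without exempting anyone, and Interim Monitoring counts failures among Trained patients who complete the study. Device removal ends a session; nothing says it ends participation. The study flowsheet is not available to check. What remains is that follow-up after a failure is implied and not spelled out.

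**Other points that stand in part**
- The per-protocol phrase is undefined, so one could argue that a person whose device was removed as the protocol directs did follow it. Untrained participants who start new exercise might also be excluded. Both are reasons to write the criteria down for both arms.
- The 20% is a guess, and with few failures the bias is small. This limits the size and leaves the structural problem in place.
- The complier-average estimate is not assumption-free. Failures may have had some device exposure at the Aim 1 session and the home fitting, and the method needs a definition of having received training and the failures' week-8 data. This argues for adding it with its assumption stated, not for treating it as the only acceptable alternative.

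**Conclusion.** The point holds for the per-protocol sensitivity analysis. On the natural reading of its definition, that analysis selects on a post-randomisation event that can occur only in the Trained arm. At the plan's tolerated failure rate the bias is about +0.08 to +0.13 SD under the assumed correlations, which is small beside the 0.96 SD design effect. It could be nil or negative, and it shrinks to 0.04 SD or less with one failure. These sizes rest on ρ = 0.7 and r = 0.3 to 0.5, which have no source in the documents, and on a 20% rate that the sponsor itself calls an estimate.

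The primary intention-to-treat analysis is not shown to be biased. It would be exposed only if failures' week-8 values were in fact not collected, and the plan implies that they are. This is an inexpensive improvement to a secondary analysis, not a flaw in the main test.

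**What to change.** 1. **Add a complier-average causal effect to the Aim 2 sensitivity analyses.** Use two-stage least squares with randomised arm as the instrument for having started HWA training, adjusted for stage and baseline velocity. The Untrained arm is kept from the device, so non-compliance is one-sided. State the assumption that randomisation affects week-8 velocity only through training, and note the brief exposure at the Aim 1 session and home fitting.
2. **If a per-protocol result is kept,** set its criteria for both arms before the data are seen. Say how safe-gait failures and Untrained participants who begin new exercise are classified, and present the result as open to selection bias.
3. **For clarity,** add one sentence confirming that participants without a safe gait attend the week-8 unassisted assessment and are analysed as randomised.

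Cost: a few sentences and a short extra analysis, with no visit beyond those already implied. The downside is a wider interval: standard error about 0.31 versus 0.26 SD at 4 failures.

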Procedures: Demographic information will be collected (i.e., age, sex, disease duration, Parkinson's medications, numbers of falls in past 6 months) and a neurologist with UPDRS motor rating certification will administer the Unified Parkinson Disease Rating Scale (UPDRS) Part III –Motor Scale²³ to assess motor impairments and determine the Hoehn and Yahr stage. A researcher who is blinded to the participants' group allocation and trained on relevant assessments will perform all outcome assessments. Assessments will be collected with participants in the ON phase at around one hour after taking their usual Parkinson's medications. *The primary outcome measure, gait velocity, will be used to validate the effectiveness of the HWA to improve gait parameters for both Aim 1 and 2.* Gait velocity (e.g., walking speed) correlates with functional ability and has been linked to clinically meaningful changes in quality of life and in home and community walking behavior.²⁴ **Aim 1:** Only participants randomized to the Trained group (n=23) will complete this part of the study to eliminate exposure of the Untrained group to the HWA device. Gait assessments will be conducted first during unassisted walking followed by HWA-assisted (i.e., wearing the HWA device) walking, with rest breaks allowed between tests. Prior to HWA-assisted walking, the researcher will select the appropriate sized HWA device, assist the participants to correctly don the device, and adjust the HWA device settings to maximize the participants' safety while walking. The PIs are experts in application and use of the HWA device (preliminary data and unshown pilot studies). Initial device settings will be symmetrical flexion and extension assist bilaterally. The research therapist will make adjustments as needed based on the response to the symmetrical assist setting. If the therapist is unable to adjust the HWA to provide a safe gait pattern the testing will be ended and the device removed. Safe gait is defined as one that results in no increase in incidence of

[figure not shown]

Figure 2. Components of the HWA Device

stumbles and/or balance loss during HWA-assisted walking as compared to unassisted walking.

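### The safe-gait interim look waits for 10 Trained patients to complete the study, about 8-9 weeks after the tenth home-fitting outcome is known; anchoring the same rule to fitting would be a cheap, low-priority improvement

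*Combined protocol and SAP*

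**What the plan says.** Interim Monitoring describes a look intended "to ensure that the rate of patients in the treatment arm unable to attain a safe gait is not unacceptably high". Its timing is: "We will evaluate the failure rate after 10 patients in the treatment arm complete the study". The boundary reads: "If 5 or more of the 10 patients fail to attain a safe gait with the device", at which point the study stops while termination is considered. With 20% taken as the acceptable rate, the plan says "we would have a 62% chance of correctly stopping the study early with an observed failure rate of 0.5", and it gives a 3% chance of stopping wrongly. A separate interim analysis at 12 months concerns data quality and analysis processes only.

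Safe gait is tested before training begins, at two points:

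- **Laboratory pre-assessment (Procedures, Aim 1).** Should the therapist prove "unable to adjust the HWA to provide a safe gait pattern the testing will be ended and the device removed". This section takes safe gait to mean no rise in stumbles or balance loss with the device compared with walking without it.
- **Home fitting (Aim 2, Intervention).** Here "the therapist will adjust the settings until a safe gait pattern is obtained". The starting point is carried over from the laboratory: "The initial setting used will be the one that produced the safest walking at the pre-assessment". Passing is the gate to training: "Participants who achieve a safe gait pattern will receive physical therapist supervised home and community-based walking training".

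The same Intervention text says that a session is ended and the device removed if a safe gait cannot be provided. Training lasts 8 weeks, and Aim 2 Outcomes places the post-assessment within one week after it.

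**The concern.** The rule watches an event that is first observed at fitting, but it is triggered by an event about two months later. While the tenth patient trains, more Trained patients can be fitted before anyone reviews the group failure rate. The plan gives no reason for the wait. It also says that the 20% rate is an estimate without preliminary data behind it, which makes an early group-level check more useful.

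The trigger is also loosely worded. A patient who fails fitting has no stated route to completing the study, so a reader cannot tell from the text how such a patient enters the 10. The boundary sentence implies that failures are among the 10, but the trigger sentence does not secure it.

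**Working it through.** **1. The plan's own figures.** Inputs from Interim Monitoring: n = 10, stop if X ≥ 5, rates 0.5 and 0.2. Exact binomial tail:

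- P(X ≥ 5 | n = 10, p = 0.5) = 0.623 (stated 62%)
- P(X ≥ 5 | n = 10, p = 0.2) = 0.033 (stated 3%)

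Both reproduce. The calculation treats 0.5 as the true failure rate. At an observed rate of 0.5 (5 of 10) the rule stops with certainty, so the word 'observed' in the plan is a slip.

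**2. The lag.** Training takes 8 weeks (Aim 2, Intervention) and the post-assessment follows within 0-1 week (Aim 2, Outcomes): 8 + (0 to 1) = 8-9 weeks from home fitting to completion. This takes the tenth patient to complete as the tenth fitted, with training starting at fitting. If completion excludes patients lost to follow-up, the plan's 20% loss means that 10 completers need on average 10/0.8 = 12.5 Trained patients, and the look comes later still.

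**3. Patients fitted during the lag.** The plan gives no accrual rate. Assume that the 23 Trained patients enter evenly over m months, so the weekly rate is 23/(m × 52/12):

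| Assumed accrual | Per week | Fitted in 8-9 weeks |
|---|---|---|
| 12 months | 0.442 | 3.5-4.0 |
| 18 months | 0.295 | 2.4-2.7 |
| 24 months | 0.221 | 1.8-2.0 |
| 36 months | 0.147 | 1.2-1.3 |

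**4. The same rule anchored to fitting.** Let f be the assumed share of eventual failures already known at home fitting. The first look stops with probability P(X ≥ 5 | n = 10, p × f):

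| f | First look, p = 0.5 | First look, p = 0.2 |
|---|---|---|
| 1.0 | 0.623 | 0.033 |
| 0.9 | 0.496 | 0.021 |
| 0.8 | 0.367 | 0.013 |

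If later failures among the same 10 are also counted and all 10 are followed to the end, the total returns to 0.623 and 0.033 whatever f is.

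**5. Incomplete follow-up of the 10.** Assume that 20% of the later failures are lost before they are seen. The effective rate is p[f + 0.8(1 − f)]. At p = 0.5:

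- f = 0.9: 0.5 × (0.9 + 0.08) = 0.49, and P(X ≥ 5) = 0.598
- f = 0.8: 0.5 × (0.8 + 0.16) = 0.48, and P(X ≥ 5) = 0.573

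Re-anchoring therefore reduces the dependence on who completes but does not remove it.

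**The case against.** The best defence is that waiting has some value. Safe gait is defined by comparing walking with and without the device. Aim 2 Outcomes reuses the Aim 1 measures after the 8 weeks and limits only the Untrained group to walking without the device, so the Trained group is apparently compared in both conditions again at post-assessment. Training also adds turning and obstacles, and a session may be ended for unsafe gait after fitting. A look at completion would capture such late failures; a single look at fitting would not. This stands, and it is why the count must run on through post-assessment.

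It is also fair that the benefit is small. Failing patients have the device removed, the stop is a pause for review, and the plan reports that all eligible participants in earlier device studies walked safely.

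A reader might go further and infer that failures drop out of the 10, so that the real chance of stopping is well below 62%. One can produce such figures. If half of the failures did not complete and everyone else did, the failure rate among completers at a true 0.5 would be 0.25/(0.25 + 0.5) = 0.333, and the chance of stopping 21%. The documents do not support this as a consequence of the plan. The boundary sentence counts failures among the 10, the Aim 2 primary analysis is by intention to treat, no differential loss is stated, and the study flowsheet (Figure 3), not available here, may cover follow-up of fitting failures. What remains is an undefined word, not a demonstrated loss of power.

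**Conclusion.** The point holds as a cheap, low-priority improvement. The look comes about 8-9 weeks later than the first information on the tenth patient allows, and completion is undefined for a patient who fails fitting. The 62% and 3% are correct for true rates of 0.5 and 0.2.

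The size is modest and rests on assumed accrual of 12-36 months: about 1-4 further Trained patients fitted during the lag. They are spared only if the early look stops the study. Even with every failure known at fitting, that is 0.623 × 1.2 to 0.623 × 4.0, or about 0.7-2.5 patients on average at a true rate of 0.5, and at most 0.033 × 4.0 = 0.13 at 0.2.

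It would be too strong to say that re-anchoring makes the stopping chances independent of who completes. With 90% or 80% of failures known at fitting and 20% of the later ones lost unseen (both assumed), the chance of stopping at 0.5 is 0.598 or 0.573.

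**What to change.** In Interim Monitoring:

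- Define the 10 as the first 10 Trained patients in whom fitting is attempted, whether or not they complete.
- Keep the 5-of-10 threshold, and look first when the tenth home-fitting outcome is known.
- Keep counting failures among the same 10 through later sessions and post-assessment, so that reaching 5 at any time triggers the same review.
- State that 62% and 3% refer to true failure rates of 0.5 and 0.2, with complete follow-up of the 10.

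The sponsor should also reconcile Procedures (Aim 1), Aim 2 Intervention and Interim Monitoring on which events count as failing to attain a safe gait: laboratory, home fitting, a later session or post-assessment. The stated 3% belongs to whichever event is chosen.

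The cost is a few sentences; threshold, data collected and staff do not change. There are two downsides: the first look rests on less follow-up than a look at completion, and the count for the 10 must be kept up to date.
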